---

## 59 Background and rationale

60 Cancer survivors experience a variety of ongoing physical and psychological symptoms associated  
61 with both disease and treatment (1,2). Additionally, cancer survivors have an increased risk of  
62 serious chronic health sequelae and comorbid conditions such as cardiovascular disease and  
63 diabetes (2). These poor health outcomes among cancer survivors have led to greater emphasis on  
64 interventions to enhance health outcomes such as health-related quality of life (HRQoL) and  
65 cancer-related fatigue (CRF) (3).

66 Aerobic training as well as resistance training are both exercise interventions associated with a  
67 number of health benefits in survivors of a variety of cancers (4–7). Thus, clinical guidelines  
68 worldwide recommend both regular aerobic- and resistance training as an essential part of the

69 rehabilitation of cancer survivors during and after active cancer treatment (1,8,9).  
70 Furthermore, aerobic training and resistance training performed at high intensity has been reported  
71 as a feasible and safe intervention for patients with various different cancer diagnosis and in  
72 different stages of cancer. It can provide objective physiological benefits as well as improve  
73 HRQoL, CRF and depression among cancer survivors (4,5,7,10–12).  
74 High Intensity Functional Training (HIFT) has been defined as a style of training that incorporates  
75 functional, multimodal movements, performed at relatively high intensity, and designed to improve  
76 parameters of general physical fitness and performance (13). In recent years HIFT has gained  
77 increasing attention in the fitness industry and in research (14), especially due to the increased  
78 popularity of the HIFT program CrossFit© (13). Recently trials, using HIFT protocols, have  
79 reported benefits in healthy adults including physiological improvements such as increased oxygen  
80 consumption, improved body composition and bone health (15,16).  
81 One identified study by Heinrich et al examined the effectiveness and feasibility of 5 weeks of  
82 HIFT among cancer survivors with a variety of cancer diagnoses. The study included 8 participants  
83 and reported that the intervention was well-received, feasible and associated with a significant  
84 improvement in emotional functioning and body composition.  
85 HIFT is viewed as a promising type of training (13,17), that has shown numerous physiological  
86 benefits (15,16,18) and has shown preliminary effectiveness and feasibility among cancer survivors  
87 (17).  
88 Furthermore, several reports and clinical guidelines recommend the prescription of exercise  
89 programs that are enjoyable and facilitates social interactions, motivation and continued  
90 participation to reduce risk of the development of comorbid conditions and late-appearing effects  
91 of cancer and its treatment (1,8,19). HIFT has been reported to be associated with higher levels of  
92 enjoyment than more traditional resistance training, and to facilitate adherence, continued  
93 participation and sense of community among healthy participants (18,20).

## 95 **Objective**

96 The primary objective of this pragmatic clinical trial is to test the feasibility of the intervention in a  
97 real world setting and secondary, to describe whether the HRQoL of the participants changes from  
98 baseline to end-point and follow up time points. Furthermore, we will investigate the association  
99 between the leisure-time HIFT and the HRQoL.

100

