163 EORTC QLQ-C-30 includes five functional domains (physical, role, cognitive, emotional and  
164 social, where higher scores represent greater function or quality of life) and three symptom scales  
165 (fatigue, pain and nausea). Functional and symptom scales range from 0 to 100. Higher values on  
166 functional scales equal a higher level of functioning. Higher values on symptom scales equal higher  
167 symptom burden. EORTC QLQ-C-30 is chosen for its established reliability and validity with  
168 specific emphasis on use in cancer populations (26, 27).

169 **GLTEQ:**

170 Leisure time physical activity (LTPA) will be assessed using an original Danish translation of the  
171 Godin-Shephard Leisure-Time Physical Activity Questionnaire (GSLTPAQ). The GSLTPAQ is  
172 frequently used in oncology research to assess LTPA.

173 The GSLTPAQ is a 4-item self-administered questionnaire. The first three questions ask for  
174 information on the number of times the respondent engages in mild, moderate and strenuous LTPA  
175 bouts of at least 15 min duration in a typical week. A score is then calculated for total leisure time  
176 based on the numerical values attributed to each of the three categories (9 for strenuous, 5 for  
177 moderate and 3 for light) multiplied by the frequency of the activity. The scores derived from this  
178 method is called a Leisure Score Index (LSI). In addition, scores obtained from moderate and  
179 strenuous physical activity can be used to classify respondents into active and insufficiently active  
180 categories.

181 A recently published systematic review by Amireault et al, supports the use of the GSLTPAQ in  
182 oncology research and the interpretation of the LSI for assessing relative change in PA among  
183 cancer survivors.

184

185 **Primary outcomes**

186 HRQoL will be evaluated using the Global Health Status/Quality of Life item from the EORTC  
187 QLQ-C-30 questionnaire. The item ranges from 0 to 100, and higher values equal higher HRQoL.

188 Time frame: for each participant at baseline + end point at 16 weeks + follow up at 3 month and 12  
189 months)

190

191

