## 192 **Secondary outcomes**

193 The secondary outcomes include functional scales (physical, role, emotional, cognitive, and social)  
194 and symptom scales (fatigue, nausea and vomiting, pain, dyspnea, insomnia, appetite loss,  
195 constipation, diarrhea, and financial difficulties) from the EORTC QLQ-C30 questionnaire).

196 In addition to the EORTC QLQ-C30 scales, leisure-time exercise will be included as a secondary  
197 outcome and will be assessed using the GSLTPAQ, including the frequency and duration of mild,  
198 moderate and strenuous exercise.

199 [Time frame for each participant: Baseline + end point at 16 weeks + follow up at 3 months and 12  
200 months]

201 Continued participation in any high intensity functional training (post-intervention HIFT) will be  
202 assessed using a single-item modified version of the (GSLTPAQ) asking participants: *During a*  
203 *typical 7-Day period (a week), how many times on the average do you do High Intensity Functional*  
204 *Training (I.E. CrossFit) for more than 15 minutes during your free time.* The participant responds  
205 by typing how many times per week, starting from zero.

206 [Time frame: for each participant at follow up at 3 month and 12 months]

207

208

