## 239 **Methods: Data collection, management and analysis**

### 240 **Data collection methods**

#### 241 **Plan for assessment and collection of outcomes**

242 All primary and secondary outcomes are participant-reported and will be administered through the  
243 online survey tool: SurveyXact. All included participants will receive an email with an electronic  
244 SurveyXact\_invitation to the baseline questionnaire the same days as providing written consent to  
245 participate in the study. On the day of the final HIFT session (week 16), the participants will receive  
246 a similar SurveyXact\_invitation with the end-point questionnaire. The three and 12-month follow up  
247 assessments will be administered in identical ways to the end-point assessment.

248

249 **Patient characteristics**

250 Demographic variables will be included in the baseline questionnaire. These will include self-  
251 reported information about: sex, body mass index, educational level, employment, smoking status  
252 and physical activity level, and will be collected together with information on cancer type, time  
253 since cancer diagnosis, time since active treatment and cancer treatment type.

254

255 **Registration of adverse events, plans to promote participant retention and complete follow  
256 up:**

257 Adverse events and reasons for drop out from discontinued participant will be collected by  
258 practising physiotherapists at CCHC.

259 To minimize non-response and loss to follow-up participants will receive a reminder by email 4 and  
260 14 days after receiving the email with end-point and follow-up questionnaire if they haven't  
261 provided their responses.

262

263 **Data management**

264 All outcomes will be handled and stored electronically on a secure server for personal data, located  
265 at the University of Copenhagen.

266 No personal data will be exported from SurveyXact without pseudonymization. Complete  
267 anonymization of all data will be done after the last follow up period. Data protection agency  
268 approval Reference number: 514-0306/19-3000

269

270 **Statistical methods**

271 Descriptive statistics will be used to summarize patient characteristics including age, sex, cancer  
272 diagnosis and type of treatment. Furthermore, leisure-time HIFT exercise and HRQoL at baseline  
273 will be summarized using the GSLTPAQ LSI score and the EORTC QLQ-C30 GH score  

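### Feasibility is the primary objective, but HRQoL is the only primary outcome, and nothing in the available text measures or analyses feasibility of the 16-week programme

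*Combined protocol and SAP*

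**What the plan says.** The Objective section ranks the aims explicitly. Feasibility comes first: "The primary objective of this pragmatic clinical trial is to test the feasibility of the intervention in a". The sentence continues: "real world setting and secondary, to describe whether the HRQoL of the participants changes from" baseline to the later time points. A third aim concerns the association between leisure-time high intensity functional training (HIFT) and HRQoL.

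Primary outcomes has one entry: "HRQoL will be evaluated using the Global Health Status/Quality of Life item from the EORTC" QLQ-C30. It is measured at baseline, week 16, and 3 and 12 months afterwards.

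Secondary outcomes begins: "The secondary outcomes include functional scales (physical, role, emotional, cognitive, and social". It goes on to nine symptom scales, leisure-time exercise by the GSLTPAQ, and continued HIFT after the programme. That last item alone has the restricted schedule "Time frame: for each participant at follow up at 3 month and 12 months".

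The section on assessment and collection of outcomes says: "All primary and secondary outcomes are participant-reported and will be administered through the" online survey tool. Under the registration of adverse events it adds: "Adverse events and reasons for drop out from discontinued participant will be collected by" the centre's physiotherapists.

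Statistical methods opens: "Descriptive statistics will be used to summarize patient characteristics including age, sex, cancer" diagnosis and treatment type. It then tests change in the outcomes and regresses HRQoL on leisure-time HIFT at each time point.

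**The concern.** A primary objective needs at least one outcome that answers it and an analysis that reports that outcome. Here the ranking of the objectives and the ranking of the outcomes point in opposite directions, and the question ranked first has neither outcome nor analysis.

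Followed literally, the study would yield significance tests of HRQoL change in one uncontrolled group, for which the Sample size section gives no power or precision rationale. Whether the programme is feasible would have to be judged afterwards. Adverse events and drop-out reasons could still be described, but which measures stand for feasibility, and over which denominators, would be chosen with the data in view.

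**Working it through.** The point is mainly textual, so the first three steps compare sections. The last two give scale.

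**1. Count the listed outcomes and ask which measure feasibility of the supervised programme.**

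| Outcome group | Number | Measures the supervised 16 weeks? |
|---|---|---|
| Global Health Status (primary) | 1 | No |
| QLQ-C30 functional scales | 5 | No |
| QLQ-C30 symptom scales | 9 | No |
| Leisure-time exercise, GSLTPAQ (counted once) | 1 | No |
| Post-intervention HIFT | 1 | No |

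Total: 1 + 5 + 9 + 1 + 1 = 17, of which 0 measure feasibility of the programme. Post-intervention HIFT is the nearest. However, it is asked only at 3 and 12 months and concerns any HIFT done in the participant's own time, so it cannot show whether the supervised sessions were attended or completed.

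**2. Look for feasibility data outside the outcome lists.** Adverse events and reasons for drop-out are recorded by physiotherapists. Neither is named as an outcome, and neither has a stated denominator or an analysis. A list of reasons for leaving is not a completion rate. The Intervention section plans two sessions a week for 16 weeks, 2 × 16 = 32 per participant, but no attendance record is mentioned in the available text. The statement that all outcomes are participant-reported also leaves no place for a staff-kept register as an outcome.

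**3. Look for a feasibility analysis.** Statistical methods contains baseline description, a paired t-test or Wilcoxon test from baseline to end-point, a repeated-measures ANOVA or Friedman test over four time points, and linear regressions. Recruitment, attendance, completion and adverse events appear in none of them.

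**4. Reproduce the plan's one relevant figure.** Sample size expects about 30 participants from 6 per month over 22 weeks. With 30.4375 days per month, 22 × 7 / 30.4375 = 5.06 months, and 6 × 5.06 = 30.4. The figure reproduces. It is an accrual forecast and is not tied to any feasibility criterion.

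**5. Precision that 30 participants would give for a feasibility proportion.** The documents give no retention figure, so the counts below are assumptions for illustration. Exact (Clopper-Pearson) limits for x out of n are the 2.5% quantile of Beta(x, n − x + 1) and the 97.5% quantile of Beta(x + 1, n − x).

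| Assumed still in programme at week 16 | Proportion | Exact 95% CI | Width (percentage points) |
|---|---|---|---|
| 18/30 | 60% | 40.6% to 77.3% | 36.7 |
| 24/30 | 80% | 61.4% to 92.3% | 30.9 |
| 27/30 | 90% | 73.5% to 97.9% | 24.4 |

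A feasibility estimate is therefore obtainable but imprecise, which is a further reason to settle its definition in advance.

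**The case against.** The strongest counter-argument is about structure. The table of contents places the primary and secondary outcomes under a patient-reported outcomes heading, and the protocol says it follows a reporting guideline for such outcomes. On that reading, Global Health Status is only the primary patient-reported outcome, and the sentence about participant-reported outcomes describes that set without excluding process measures. This is a fair reading and it softens the charge of reversal. It does not fill the gap, because no other section in the available text supplies a feasibility outcome.

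Feasibility-type data are also planned. Adverse events and drop-out reasons are collected prospectively, and with one consecutively enrolled group the enrolled participants are the natural denominator. Continued HIFT may reflect how well the activity is sustained. All of this is true, but the denominator and the analysis remain unstated, and delivery of the 16 weeks is still not measured.

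The study calls itself exploratory. That is a good reason not to insist on a success threshold. The protocol uses it to explain the absence of a power calculation; it does not justify leaving the main question without any measure.

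Finally, figures 1 to 3 and the text of Appendix 1 were not available, so the statement of absence is limited to the text that was. The sections where a feasibility outcome would be expected (objective, outcomes, data collection, statistical methods) are all present.

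**Conclusion.** The concern holds and should be fixed. The objective ranked first has no outcome and no analysis in the available text: 0 of 17 listed outcomes measure feasibility of the supervised programme. This goes beyond missing detail, because carrying out the plan exactly would not give a pre-specified answer to its own primary question. The conclusion rests on the wording of the sections and not on the illustrative intervals. It does not depend on whether 'primary' means primary overall or primary among patient-reported outcomes.

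**What to change.** The investigators should choose one of two routes before the data are seen.

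**Option 1: keep feasibility primary.** Make the following the primary outcome set.

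- Sessions attended per participant out of the 32 planned, as median and interquartile range.
- Proportion of enrolled participants still in the programme at week 16, with exact 95% CI. What counts as still in the programme needs a written definition, so that a single late session does not decide it by default.
- Proportion of enrolled participants with an adverse event, with exact 95% CI, once the investigators have stated the definition and collection window, which the available text does not give.
- Number consenting out of those eligible and asked. This should be reported as study recruitment, not as uptake of HIFT, because choosing HIFT is itself an eligibility criterion.

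A success threshold is optional in an exploratory study; if one is used, the investigators should fix it in advance. If none is used, the objective is better worded as estimating feasibility than as testing it. Global Health Status becomes the first secondary outcome, the sentence that all outcomes are participant-reported is amended, and these analyses are added to Statistical methods.

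Cost: an attendance list and a recruitment log, kept by physiotherapists who already run the sessions, hold the recruitment visit and record adverse events and drop-out reasons. HRQoL loses its primary label.

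**Option 2: make HRQoL primary.** Reorder the Objective section to match the outcomes, and report drop-out and adverse events descriptively with all enrolled participants as denominator.

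Cost: a small descriptive analysis. Feasibility is no longer claimed as the main question, and HRQoL becomes the main question although Sample size gives no power or precision rationale for it.

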## 101 **Methods: Participants interventions and outcomes**

102 This study protocol is reported according to the Guidelines for Inclusion of Patient-Reported  
103 Outcomes in Clinical Trial Protocols (SPIRIT-PRO) Extension.

104

### 118 **Eligibility criteria**

119 Due to the pragmatic design of this study, only few inclusion- and exclusion criteria will be applied.  
120 Patients will be considered eligible for inclusion when they; 1) are at least 18 years old, 2) are  
121 referred to the centre for cancer rehabilitation from any hospital or private practising general  
122 practitioner in the Capital Region in Denmark, 3) Choosing to participate in group based high  
123 intensity functional training that is offered at CCHC as part of their physical rehabilitation.  
124 Eligibility for participation in this study will be regardless of cancer treatment and the stage of the  
125 cancer. Thus, both patients undergoing active cancer treatment, patient who have completed active  
126 treatment as well as chronic cancer survivors will be considered eligible for participation in this  
127 study.

128 The following exclusion criteria will be applied for this study: 1) Not able to reply to the  
129 questionnaire due to mental impairment, 2) Patients who are not able to read and understand

130 Danish, 3) Patients who does not have an e-mail address because of the application of online-based  
131 questionnaires.

132

### 133 Intervention

134 The exercise intervention for this study will be HIFT, as defined by Feito et al and described in the  
135 introduction of this study protocol (13). The program design and template will be based on the  
136 principles of the HIFT program called CrossFit®. CrossFit is described as a strength and  
137 conditioning program that focuses on “constantly varying functional movements, performed at a  
138 relatively high intensity” (23). CrossFit training includes a variety of elements from gymnastics  
139 (e.g., floor, bar and ring exercises), weightlifting exercises (e.g., squats, cleans, snatches and presses  
140 with a barbell, dumbbell or kettlebell), and cardiovascular activities (e.g., running or rowing) (24).

141  
142 All group training sessions will take place in a clinical setting at CCHC.

143 The full exercise protocol template is designed as a 38-week HIFT program, as the inclusion of  
144 participants will be consecutive. All participants will complete 16 weeks of twice weekly group-  
145 based HIFT sessions, under the supervision of two physiotherapists, specifically trained to deliver  
146 the HIFT program. Given the consecutive nature of this inclusion process, the participants will  
147 initiate the group-based training at different dates between august 5th 2019 and January 5th 2019 (see  
148 figure 2 for process of HIFT program implementation and figure 3 for timeline of the study period  
149 with important dates).

150

151 Each training session will last for one hour and 15 minutes and will include a general warmup, a  
152 strength-focused section including 1-3 exercises and a aerobic-focused workout.

153 The exercise program is not developed to include a general progression in terms of resistance,  
154 intensity or volume over the cause of 38 weeks. An exercise compendium will be developed to meet  
155 one of the key principles of CrossFit, that is scalability (25). The compendium will include  
156 movement standards as well as progressions and regressions of all included exercises. This is to  
157 assist the supervising physiotherapists in choosing the relevant level of intensity and exercise  
158 difficulty for each participant, and to allow for individual progression over the cause of the 16-week  
159 exercise intervention period for each participant.

160

161 **Patient-reported outcomes**

162 **EORTC:**

163 EORTC QLQ-C-30 includes five functional domains (physical, role, cognitive, emotional and  
164 social, where higher scores represent greater function or quality of life) and three symptom scales  
165 (fatigue, pain and nausea). Functional and symptom scales range from 0 to 100. Higher values on  
166 functional scales equal a higher level of functioning. Higher values on symptom scales equal higher  
167 symptom burden. EORTC QLQ-C-30 is chosen for its established reliability and validity with  
168 specific emphasis on use in cancer populations (26, 27).

169 **GLTEQ:**

170 Leisure time physical activity (LTPA) will be assessed using an original Danish translation of the  
171 Godin-Shephard Leisure-Time Physical Activity Questionnaire (GSLTPAQ). The GSLTPAQ is  
172 frequently used in oncology research to assess LTPA.

173 The GSLTPAQ is a 4-item self-administered questionnaire. The first three questions ask for  
174 information on the number of times the respondent engages in mild, moderate and strenuous LTPA  
175 bouts of at least 15 min duration in a typical week. A score is then calculated for total leisure time  
176 based on the numerical values attributed to each of the three categories (9 for strenuous, 5 for  
177 moderate and 3 for light) multiplied by the frequency of the activity. The scores derived from this  
178 method is called a Leisure Score Index (LSI). In addition, scores obtained from moderate and  
179 strenuous physical activity can be used to classify respondents into active and insufficiently active  
180 categories.

181 A recently published systematic review by Amireault et al, supports the use of the GSLTPAQ in  
182 oncology research and the interpretation of the LSI for assessing relative change in PA among  
183 cancer survivors.

184

185 **Primary outcomes**

186 HRQoL will be evaluated using the Global Health Status/Quality of Life item from the EORTC  
187 QLQ-C-30 questionnaire. The item ranges from 0 to 100, and higher values equal higher HRQoL.

188 Time frame: for each participant at baseline + end point at 16 weeks + follow up at 3 month and 12  
189 months)

190

191

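### The protocol does not say whether the supervised centre sessions count as leisure-time activity in the GSLTPAQ, so the week-16 leisure score can rise, and later fall, because of the intervention itself

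*Combined protocol and SAP*

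**What the plan says.** The Patient-reported outcomes section (GLTEQ) describes the GSLTPAQ as asking for "information on the number of times the respondent engages in mild, moderate and strenuous LTPA", in "bouts of at least 15 min duration in a typical week". The LSI multiplies each weekly frequency by a weight and is "based on the numerical values attributed to each of the three categories (9 for strenuous, 5 for" moderate and 3 for light. The same section says that the moderate and strenuous scores can also be used to class respondents as active or insufficiently active.

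The Secondary outcomes section makes leisure-time exercise by GSLTPAQ a secondary outcome at baseline, week 16, 3 months and 12 months. It adds a single item on high intensity functional training (HIFT) done in one's free time, asked at 3 and 12 months only.

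On the programme, the Intervention section says "All participants will complete 16 weeks of twice weekly group" sessions and "Each training session will last for one hour and 15 minutes". It describes the training model as "relatively high intensity", with the level chosen for each participant.

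On timing, the Participation timeline places baseline in the four days before supervised training begins and follow-up 3 and 12 months after it is completed. The end-point form goes out on the day of the last session: "participate in the study. On the day of the final HIFT session (week 16), the participants will receive" the invitation.

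The Statistical methods section plans, for each outcome, a baseline to end-point test (paired t, or Wilcoxon signed-ranks if residuals are not normal) and a four-level repeated-measures test. It also plans a regression of HRQoL on leisure-time HIFT at each time point.

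**The concern.** The trial's own sessions meet the bout-length criterion easily and recur every week for 16 weeks. Someone asked about a typical week on the last training day could reasonably include them. Of the four assessments, week 16 is the one at which every participant has just been in the programme.

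If some participants include the sessions, the week-16 LSI mixes attendance at the intervention with leisure activity. A person whose leisure activity never changed would appear more active at week 16 and would then appear to drop back at 3 months. Both the baseline to end-point test and the four-level test use that value. The design is single-group, so no comparator would reveal the artefact. Once the answers are in, an analyst cannot separate supervised from leisure bouts, because the free-time HIFT item is not asked at week 16.

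**Working it through.** **Inputs from the protocol**
- Supervised sessions: 2 per week, 75 minutes each, for 16 weeks (Intervention).
- Bout threshold 15 minutes; weights 9, 5 and 3 (Patient-reported outcomes).
- Anticipated number: about 30 (Sample size).
- Significance level 0.05 (Statistical methods); two-sided testing is assumed, as the sidedness is not stated.

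**Inputs assumed**
- SD of the LSI change: 20 to 30 points. The protocol gives none.
- Share of participants who count both sessions: 25%, 50% or 100%.
- No true change in leisure activity, and all 30 participants give complete pairs.

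**Step 1: the plan's own figure.** At 6 participants per month, 5 months gives 6 × 5 = 30, and 22 weeks gives 6 × 22 / (52/12) = 30.5. The stated figure of about 30 is reproduced.

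**Step 2: points per participant who counts both sessions.** Contribution = sessions per week × weight.
- Rated strenuous: 2 × 9 = 18
- Rated moderate: 2 × 5 = 10
- Rated light: 2 × 3 = 6

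These three figures use protocol numbers only. Participants who stop the sessions would lose the same amount at 3 months.

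**Step 3: mean shift.** If a share p counts the sessions and each gains c points, the mean shift is c × p. For c = 18 that is 4.5, 9 or 18 points at 25%, 50% or 100%. For c = 10 it is 2.5, 5 or 10, and for c = 6 it is 1.5, 3 or 6.

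**Step 4: rejection probability of the paired t-test.** Counting by only some participants adds variance, so the total SD is √(SD² + c² p(1 − p)). The noncentrality is c p / (total SD / √30), with 29 degrees of freedom and critical value 2.045.

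Example: c = 18, p = 0.5, SD 20. Total SD = √(400 + 324 × 0.25) = 21.9; noncentrality = 9 / (21.9 / √30) = 2.25; rejection probability = 58%.

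| Session rating (points) | SD of change | 25% count | 50% count | 100% count |
|---|---|---|---|---|
| Strenuous (18) | 20 | 20% | 58% | 99.7% |
| Strenuous (18) | 30 | 12% | 33% | 89% |
| Moderate (10) | 20 | 10% | 25% | 75% |
| Moderate (10) | 30 | 7% | 14% | 42% |
| Light (6) | 20 | 7% | 12% | 36% |
| Light (6) | 30 | 6% | 8% | 19% |

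The nominal rate is 5% throughout.

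**Step 5: the week-16 regression.** The regressor is called leisure-time HIFT. The HIFT item exists only at 3 and 12 months, while the Statistical methods section summarises leisure-time HIFT at baseline by the LSI. The protocol does not settle which variable would be used at week 16.

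**The case against.** The strongest reply is that the instrument already excludes the sessions. It is about leisure time, and these sessions are rehabilitation after referral, at a municipal centre, led by two physiotherapists. Many respondents may leave them out, and the Danish form may say so. This stands as a limit on likelihood. It does not close the gap: leisure time is not defined for centre-based training, participants themselves choose to join it, and the form is not reproduced. A reader might infer that participants will count the sessions; the documents show only that they can.

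A reader might also take 18 points as the size of the bias. That is the upper end. It needs both sessions to be counted, both to be rated strenuous, and neither to have replaced other activity. Patients on active treatment are eligible and the level is individual, so 10 or 6 points is just as possible.

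The t-test rates are illustrative. The plan switches to the Wilcoxon test when residuals are not normal, and a mixture of people who do and do not count the sessions could contribute to that.

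A further inference would be that the distortion is confined to week 16. That is not established. The programme template runs 38 weeks (22 of inclusion plus 16), and the earliest starters reach their 3-month follow-up at about week 16 + 13 = 29. The documents do not say whether they may still be attending.

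Finally, this is one secondary outcome in an exploratory study without a power calculation. That is correct and limits the weight of the point.

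**Conclusion.** The point holds as a gap in the outcome definition with an inexpensive remedy. The protocol leaves open whether supervised sessions enter the week-16 LSI. Each participant who counts both adds 18, 10 or 6 points, depending on the intensity rating, without any change in leisure activity. Under the stated assumptions, the chance of a spurious significant change from baseline lies between about 6% and 99.7%. The width of that range reflects the unknown SD, counting share and intensity rating.

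Two stronger conclusions are not supported. The week-16 association with HRQoL is affected only if the LSI is the variable used there, which the protocol leaves unclear. The primary outcome, global health status/quality of life, does not use the LSI and is not affected. Nor does the point require the main LSI comparison to move to 3 or 12 months; that would be a preference.

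**What to change.** Keep the standard GSLTPAQ items and add one question to the week-16 form: how many supervised centre sessions per week were included in the answers, and at which intensity. Define the secondary outcome as LSI without supervised sessions, that is, reported LSI minus 9, 5 or 3 points for each included session rated strenuous, moderate or light. Apply the same exclusion if the active/insufficiently active classification is used. Keep the planned baseline to end-point contrast, on the corrected LSI.

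An alternative is an instruction to leave out supervised centre sessions. It should then appear at all four time points so that the form does not differ between visits.

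The analysis section should also name the variable used in the week-16 regression.

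The cost is one extra online question, one or two sentences in the analysis plan, and a small departure from the standard form. If week-16 data have already been collected, report the week-16 LSI with a caveat that it may include the supervised sessions.
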